1.1 Does the protocol specify timelines for				
1.1.1 Start of data collection ¹				2; 4
1.1.2 End of data collection ²				2; 4
1.1.3 Progress report(s)				-
1.1.4 Interim report(s)				-
1.1.5 Registration in the EU PAS Register®				2; 4
1.1.6 Final report of study results.				2; 4

Comments:

--

Section 2: Research question	Yes	No	N/A	Section Number
2.1 Does the formulation of the research question and objectives clearly explain:				5
2.1.1 Why the study is conducted? (e.g. to address an important public health concern, a risk identified in the risk management plan, an emerging safety issue)				5
2.1.2 The objective(s) of the study?				6
2.1.3 The target population? (i.e. population or subgroup to whom the study results are intended to be generalised)				7.2
2.1.4 Which hypothesis(-es) is (are) to be tested?				6
2.1.5 If applicable, that there is no a priori hypothesis?				-

Comments:

--

¹ Date from which information on the first study is first recorded in the study dataset or, in the case of secondary use of data, the date from which data extraction starts.

² Date from which the analytical dataset is completely available.

Section 3: Study design	Yes	No	N/A	Section Number
3.1 Is the study design described? (e.g. cohort, case-control, cross-sectional, other design)				7.1
3.2 Does the protocol specify whether the study is based on primary, secondary or combined data collection?				7.4.1
3.3 Does the protocol specify measures of occurrence? (e.g., rate, risk, prevalence)				7.5.2; 7.5.6
3.4 Does the protocol specify measure(s) of association? (e.g. risk, odds ratio, excess risk, rate ratio, hazard ratio, risk/rate difference, number needed to harm (NNH))				7.5.2; 7.5.6
3.5 Does the protocol describe the approach for the collection and reporting of adverse events/adverse reactions? (e.g. adverse events that will not be collected in case of primary data collection)				9

Comments:

--

Section 4: Source and study populations	Yes	No	N/A	Section Number
4.1 Is the source population described?				7.2 7.4
4.2 Is the planned study population defined in terms of:				
4.2.1 Study time period				7.2; 7.4
4.2.2 Age and sex				7.3.3
4.2.3 Country of origin				7.3.3
4.2.4 Disease/indication				7.3.2; 7.3.3
4.2.5 Duration of follow-up				7.2; 7.5.1, 7.5.4
4.3 Does the protocol define how the study population will be sampled from the source population? (e.g. event or inclusion/exclusion criteria)				7.2

Comments:

--

Section 5: Exposure definition and measurement	Yes	No	N/A	Section Number
5.1 Does the protocol describe how the study exposure is defined and measured? (e.g. operational details for defining and categorising exposure, measurement of dose and duration of drug exposure)				7.3.1
5.2 Does the protocol address the validity of the exposure measurement? (e.g. precision, accuracy, use of validation sub-study)				7.7.6; 7.8
5.3 Is exposure categorised according to time windows?				7.3.1; 7.8
5.4 Is intensity of exposure addressed? (e.g. dose, duration)				7.3.1
5.5 Is exposure categorised based on biological mechanism of action and taking into account the pharmacokinetics and pharmacodynamics of the drug?				7.3.1
5.6 Is (are) (an) appropriate comparator(s) identified?				7.3.1; 7.5.3

Comments:

--

Section 6: Outcome definition and measurement	Yes	No	N/A	Section Number
6.1 Does the protocol specify the primary and secondary (if applicable) outcome(s) to be investigated?				7.3.2
6.2 Does the protocol describe how the outcomes are defined and measured?				7.3.2
6.3 Does the protocol address the validity of outcome measurement? (e.g. precision, accuracy, sensitivity, specificity, positive predictive value, use of validation sub-study)				7.8
6.4 Does the protocol describe specific outcomes relevant for Health Technology Assessment? (e.g. HRQoL, QALYs, DALYS, health care services utilisation, burden of disease or treatment, compliance, disease management)				

Comments:

--

Section 7: Bias	Yes	No	N/A	Section Number
7.1 Does the protocol address ways to measure confounding? (e.g. confounding by indication)				7.3.3
7.2 Does the protocol address selection bias? (e.g. healthy user/adherer bias)				7.4; 7.9
7.3 Does the protocol address information bias? (e.g. misclassification of exposure and outcomes, time-related bias)				7.3.1; 7.3.3; 7.7; 7.9

Comments:

--

Section 8: Effect measure modification	Yes	No	N/A	Section Number
8.1 Does the protocol address effect modifiers? (e.g. collection of data on known effect modifiers, subgroup analyses, anticipated direction of effect)				7.3.3; Table 4; 7.7

Comments:

Regarding 8.1: we stratify by age and in a sensitivity analysis by country.

Section 9: Data sources	Yes	No	N/A	Section Number
9.1 Does the protocol describe the data source(s) used in the study for the ascertainment of:				
9.1.1 Exposure? (e.g. pharmacy dispensing, general practice prescribing, claims data, self-report, face-to-face interview)				7.3.1; 7.4
9.1.2 Outcomes? (e.g. clinical records, laboratory markers or values, claims data, self-report, patient interview including scales and questionnaires, vital statistics)				7.3.2; 7.4
9.1.3 Covariates and other characteristics?				7.3.3- 7.3.4; 7.4
9.2 Does the protocol describe the information available from the data source(s) on:				
9.2.1 Exposure? (e.g. date of dispensing, drug quantity, dose, number of days of supply prescription, daily dosage, prescriber)				7.3.1; 7.4
9.2.2 Outcomes? (e.g. date of occurrence, multiple event, severity measures related to event)				7.3.2; 7.4

Section 9: Data sources	Yes	No	N/A	Section Number
9.2.3 Covariates and other characteristics? (e.g. age, sex, clinical and drug use history, co-morbidity, co-medications, lifestyle)				7.3.3-7.3.4; 7.4
9.3 Is a coding system described for:				
9.3.1 Exposure? (e.g. WHO Drug Dictionary, Anatomical Therapeutic Chemical (ATC) Classification System)				7.3.1
9.3.2 Outcomes? (e.g. International Classification of Diseases (ICD), Medical Dictionary for Regulatory Activities (MedDRA))				7.3.2
9.3.3 Covariates and other characteristics?				7.3.3-7.3.4
9.4 Is a linkage method between data sources described? (e.g. based on a unique identifier or other)				7.4

Comments:

--

Section 10: Analysis plan	Yes	No	N/A	Section Number
10.1 Are the statistical methods and the reason for their choice described?				7.7
10.2 Is study size and/or statistical precision estimated?				7.5.1; 7.5.5; 7.5.6
10.3 Are descriptive analyses included?				7.7
10.4 Are stratified analyses included?				7.7
10.5 Does the plan describe methods for analytic control of confounding?				7.7
10.6 Does the plan describe methods for analytic control of outcome misclassification?				7.7
10.7 Does the plan describe methods for handling missing data?				7.6
10.8 Are relevant sensitivity analyses described?				7.7.6

Comments:

Effect modification will be evaluated using stratified analyses by age. Different methods for evaluating effect modification have not been discussed.

Section 11: Data management and quality control	Yes	No	N/A	Section Number
11.1 Does the protocol provide information on data storage? (e.g. software and IT environment, database maintenance and anti-fraud protection, archiving)				7.6
11.2 Are methods of quality assurance described?				7.6
11.3 Is there a system in place for independent review of study results?				-

Comments:

--

Section 12: Limitations	Yes	No	N/A	Section Number
12.1 Does the protocol discuss the impact on the study results of:				
12.1.1 Selection bias?				7.9
12.1.2 Information bias?				7.9
12.1.3 Residual/unmeasured confounding? (e.g. anticipated direction and magnitude of such biases, validation sub-study, use of validation and external data, analytical methods).				7.9
12.2 Does the protocol discuss study feasibility? (e.g. study size, anticipated exposure uptake, duration of follow-up in a cohort study, patient recruitment, precision of the estimates)				7.5.2

Comments:

--

Section 13: Ethical/data protection issues	Yes	No	N/A	Section Number
13.1 Have requirements of Ethics Committee/ Institutional Review Board been described?				8
13.2 Has any outcome of an ethical review procedure been addressed?				-
13.3 Have data protection requirements been described?				8

Comments:

--

Section 14: Amendments and deviations	Yes	No	N/A	Section Number
14.1 Does the protocol include a section to document amendments and deviations?				Summary of Changes

Comments:

Summary of changes is located before The table of contents

Section 15: Plans for communication of study results	Yes	No	N/A	Section Number
15.1 Are plans described for communicating study results (e.g. to regulatory authorities)?				10
15.2 Are plans described for disseminating study results externally, including publication?				10

Comments:

Name of the main author of the protocol:

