6 RESEARCH QUESTION AND OBJECTIVES

The research question is to examine the associations between DL use and seizures, SVT, and A-fib/flu in the general population.

Primary hypotheses (stated as null-hypotheses)

- There is no association between current DL use and first seizure.
- There is no association between current DL use and SVT.
- There is no association between current DL use and A-fib/flu.

Primary objectives

- Describe the use of DL during the study period in the general population overall and stratified by country, age, gender, calendar year, seasonality, severity of rhinitis, asthmatic status, and chronic urticaria status.
- Describe the IRs of the following outcomes in the general population:
 - Incident diagnosis of seizure;
 - Incident diagnosis of SVT; and

- Incident diagnosis of A-fib/flu.
- Compare the risk of incident seizure among persons while currently exposed to DL to the risk among the same persons while unexposed to DL for the total DL population and stratified by age, while adjusting for relevant confounding factors.
- Compare the risk of incident SVT among persons while currently exposed to DL to the risk among the same persons while unexposed to DL for the total DL population and stratified by age, while adjusting for relevant confounding factors.
- Compare the risk of incident A-fib/flu among persons while currently exposed to DL to the risk among the same persons while unexposed to DL for the total DL population and stratified by age, while adjusting for relevant confounding factors.

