A descriptive analysis of DL use in the general population. To describe DL use in the general population, we will identify both prevalent and incident users of DL and describe the distribution of the number of redeemed DL prescriptions for the total population and stratified by country, age, sex, calendar year, seasonality, severity of rhinitis, asthmatic status, and chronic urticaria status.

2. Substudies 2A and 2B

A descriptive analysis of the IR of first seizure overall in the general population and stratified by country, sex, and age will be conducted (2A).

Among persons ever dispensed DL, the association between exposure to DL use and first seizure will be evaluated using Poisson regression of the IR of first seizure for the total population and stratified by age when accounting for confounding factors (2B).

3. Substudies 3A and 3B

Descriptive analysis of the IR of SVT overall in the general population and stratified by country, sex, and age will be conducted (3A).

Among persons ever dispensed DL, the association between exposure to DL use and first SVT will be evaluated using Poisson regression of the IR of first SVT for the total population and stratified by age when accounting for confounding factors (3B).

4. Substudies 4A and 4B

Descriptive analysis of the IR of A-fib/flu overall in the general population and stratified by country, sex, and age will be conducted (4A).

Among persons ever dispensed DL, the association between exposure to DL use and first A-fib/flu will be evaluated using Poisson regression of the IR of first A-fib/flu for the total population and stratified by age when accounting for confounding factors (4B).

5. Supplementary analyses

In total, 10 supplementary analyses will be performed to examine the robustness of the results. These are described in further details in section 7.7.6 of the protocol as well as in the SAP.

7.2 **Setting**

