7.5.5 Statistical parameters and assumptions

The minimum incidence rate ratio, $IRR > 1$, that can be detected is calculated using the following parameter values and assumptions:

Significance level, α : 0.05

Power, $1-\beta$: 0.80

1-sided test

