7.5.6 Example of calculating the minimum detectable IRR

The mean number of DL prescriptions in the age group 0–4 years is 1.50 prescriptions. This gives an exposure period of $(1.50 * 4 \text{ weeks}) + 4 \text{ weeks} = 10 \text{ weeks}$. In this age group, 20,000 children have redeemed DL (i.e., the fixed sample size for this age group). Due to the exposure period of 10 weeks in this group, the proportion of the time exposed to DL is $10 \text{ weeks} / 52 \text{ weeks per year} = 19\%$. The background annual rate of seizures is 65/100,000 in this age group. It is assumed that individuals in this age group will be included in the study for an average of 2 years. When using a 1-sided test, significance level of 5% and power of 80%, the minimum detectable IRR will be 3.0.

Table 6 The minimum detectable incidence rate ratio (IRR>1) was calculated based on the Nordic population of SL users with at least one prescription of DL per year. Incidence rate (IR) of seizures is based on Hauser & Beghi (2008) [Hauser, W. A. and Beghi, E. 2008]. A 1-sided test, significance level of 5% and power of 80% have been used.

Age group (years)	Annual IR of seizures among unexposed individuals per 100,000 person-years	Mean number of individuals with at least one annual DL prescription in the Nordic countries	Estimated number of weeks exposed based on mean number of DL prescriptions per person	Minimum detectable IRR t=2 and 6 years (for age 0-4 years and age ≥5 years)
0-4	65	20,000	10.00	3.0
5-19	50	86,000	10.48	1.5
20-64	40	215,000	11.12	1.3
≥65	40	44,500	13.20	1.7

Table 7 The minimum detectable incidence rate ratio (IRR>1) was calculated based on the Nordic population of DL users with at least one prescription of DL per year. Incidence rate (IR) of SVT is based on Orejarena et al. (1998) [Orejarena, L. A., et al 1998]. A 1-sided test, significance level of 5% and power of 80% have been used.

Age group (years)	Annual IR of SVT among unexposed individuals per 100,000 person-years	Mean number of individuals with at least one annual DL prescription in the Nordic countries	Estimated number of weeks exposed based on mean number of DL prescriptions per person	Minimum detectable IRR t=2 and 6 years (for age 0-4 years and age ≥5 years)
0-4	13	20,000	10.00	8.2
5-19	13	86,000	10.48	2.1
20-64	27	215,000	11.12	1.4
≥65	122	44,500	13.20	1.4

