A cohort study among ever-DL users analyzing the association between exposed and unexposed time and first seizures will be performed for the total population and stratified by age. Current use (i.e., “exposed” period) will be defined for each prescription as days’ supply plus a 4 week grace period to account for intermittent use and a possible wash-out effect. Unexposed time will be defined as the period starting 26 weeks from the dispensing date of the prior DL prescription until the next DL prescription redemption, if any. A person who has redeemed at least one prescription of DL is included in the cohort and enters the cohort at the date of first prescription redemption. Study individuals are followed until occurrence of a seizure; occurrence of one of the conditions described in section 7.2.2; 31 December 2015; emigration; or death, whichever comes first. The association between exposure to DL and first seizure will be evaluated using Poisson regression of the IR of first seizure, and the measure of effect is the IRR. A person with prescription redemption of DL in Norway and Sweden within the first 6 months after establishment of the prescriptions registers will not be included in order to account for truncation bias. In addition we exclude persons with DL prescription redemptions within 6 months after immigrating to Denmark, Finland, Norway, or Sweden. The analyses will be adjusted for confounders identified from the DAG (i.e., country, age, sex, calendar year, seasonality, severity of rhinitis, asthmatic status, and chronic urticaria status) (Table 4). We will evaluate whether age can be included as a continuous variable by examining the assumption of linearity. Alternatively, age will be included as a categorical variable.

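### The only method named for effect modification by age is separate age-stratum IRRs, which neither estimate nor test the difference between ages

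*Protocol*

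**What the plan says.** Two comments in the ENCePP checklist (protocol Annex 2) address effect modification. Under Section 8: "Regarding 8.1: we stratify by age and in a sensitivity analysis by country". Under Section 10, on the analysis plan: "Effect modification will be evaluated using stratified analyses by age. Different methods for evaluating effect modification have not been discussed".

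The body of the protocol agrees. The association objectives in Section 6 compare exposed with unexposed time "for the total DL population and stratified by age, while adjusting for relevant confounding factors". For seizures, Section 7.1 says the association will be "evaluated using Poisson regression of the IR of first seizure for the total population and stratified by age when accounting for confounding factors", and 7.7.2 repeats this. Sections 7.7.3 and 7.7.4 use the same scheme for SVT and A-fib/flu. This protocol names no exposure-by-age term, heterogeneity test or ratio of IRRs between age groups.

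**The concern.** Effect modification is a difference between stratum-specific IRRs. Four separate stratum analyses give four estimates, but no estimate of how far they differ and no interval for that difference. With strata this unequal, which of them reach significance mainly reflects event counts.

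The question will be asked. Section 5 cites seizures in four children and rising paediatric use, and says the reported cardiac cases were spread across all age groups, not only children. The age-stratified IRRs are part of the primary objectives, and the results go to the EU health authorities. Readers will compare children with adults. Without a stated contrast, they may do so by noting which stratum is significant, and could conclude wrongly that children are spared or specially affected.

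**Working it through.** **Inputs, all from the protocol, in the order 0-4, 5-19, 20-64, ≥65 years**
- Users n: 20,000; 86,000; 215,000; 44,500 (7.5.1)
- Exposed weeks per year: 10.00; 10.48; 11.12; 13.20 (7.5.2). Dividing by 52 gives E.
- Follow-up t: 2, 6, 6, 6 years (7.5.4)
- Seizure rates: 65, 50, 40, 40 per 100,000 person-years. SVT rates: 13, 13, 27, 122 (7.5.3). A-fib rates at 0-4 and 5-19: 1.6 and 3.8 (Table 8).

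**Step 1: reproduce the protocol's own figures.** The Annex 7 formula, (p1 − p2)² = (Zα + Zβ)² [p1q1/(En) + p2q2/((1 − E)n)] with p2 = 1 − exp(−rate × t), one-sided 5% and 80% power, gives detectable seizure IRRs of 3.00, 1.45, 1.30 and 1.68. Table 6 prints 3.0, 1.5, 1.3 and 1.7, so the inputs are read correctly.

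**Step 2: expected events at background rates (n × t × rate).**
- Seizures: 20,000 × 2 × 65/100,000 = 26; 86,000 × 6 × 50/100,000 = 258; 215,000 × 6 × 40/100,000 = 516; 44,500 × 6 × 40/100,000 = 106.8.
- SVT, in the same way: 5.2, 67, 348 and 326.
- A-fib at 0-4: 20,000 × 2 × 1.6/100,000 = 0.64. At 5-19: 86,000 × 6 × 3.8/100,000 = 19.6.

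**Step 3: how often the strata give mixed verdicts under a common IRR.** Poisson counts were simulated with exposed mean n × t × rate × E × IRR and unexposed mean n × t × rate × (1 − E). Each stratum was tested for a raised IRR with a two-sided 5% likelihood-ratio test. A mixed verdict means at least one stratum significantly raised and at least one not. The common IRR is an assumption, so a range is shown for seizures:

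| Common IRR | Mixed verdict |
|---|---|
| 1.0 | 9% |
| 1.1 | 30% |
| 1.2 | 64% |
| 1.3 | 90% |
| 1.5 | 94% |
| 2.0 | 62% |
| 3.0 | 16% |

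At IRR 1.3 the four strata are significant with probability about 8%, 44%, 75% and 24%. For SVT at a common IRR of 1.5 the verdict is mixed in 98%.

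The result depends on the rule. With one-sided tests, or counting significance in either direction, the figure at IRR 1.0 is about 17-19%. Judged instead by whether any pair of 95% CIs fails to overlap, disagreement at a common IRR between 1.0 and 2.0 occurs in only about 3-4%.

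**Step 4: the alternative on the same data.** A 3-df likelihood-ratio test of one common IRR against four separate IRRs gives a false signal in 5-6% at every common seizure IRR tried. Its power is:

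| True departure (IRR 1 in the other groups) | Power |
|---|---|
| Seizure IRR 2 at 5-19 only | 97% |
| Seizure IRR 3 at 0-4 only | 70% |
| Seizure IRR 2 at 0-4 only | about 27% |
| Seizure IRR 1.5 at 0-4 only | 11% |
| SVT IRR 3 at 0-4 only | about 19% |
| SVT IRR 2 at 0-4 only | 10% |

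**The case against.** *The protocol never says strata will be compared by significance.* Correct. It plans stratum IRRs, and stratified IRRs with CIs are a standard way to display effect modification. The percentages in Step 3 show what one likely reading would do, not what the plan prescribes. What stands is that the protocol names stratification as its method and offers no measure of the difference that a reader could use instead.

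*The checklist comment may mean only that other methods are not discussed in this document.* That is fair. The comment does not show that an interaction test was considered and rejected, and it does not rule one out.

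*A heterogeneity test belongs in the SAP.* It may be there; the SAP was not available for this review. But 7.7 refers to the SAP the details of the supplementary analyses, whereas the age-stratified IRRs belong to the primary objectives and are set out in the protocol. The point concerns a stated choice, not a missing detail.

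*No hypothesis about age exists, and the weak strata are disclosed.* Both are true. Tables 6-8 give detectable IRRs by age, and 7.9 concedes the limits in the youngest group for A-fib and SVT. This lowers the severity. It does not remove the point, because the checklist itself says effect modification by age will be evaluated.

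*Making the test a gate would do harm.* This stands. With 10-27% power for a doubling of SVT or seizure risk confined to 0-4 years, allowing a statement of an age difference only after a significant test would usually bar reporting of a real paediatric excess. A model with only the exposure term varying by age would also force common confounder effects across ages, which separate strata avoid.

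**Conclusion.** The point holds as a cheap improvement. The only method this protocol names for effect modification by age gives neither an estimate nor a test of the difference between ages, and the strata are very unequal, from about 26 to 516 expected seizures.

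A reader might infer that the age strata will appear to disagree about 90% of the time whenever the true IRR is the same at every age. The documents do not support that. The figure needs a significance-comparison rule that the protocol does not state, and a common seizure IRR near 1.3-1.5 that appears nowhere as an assumption. Under the protocol's own null hypothesis it is about 9% on the rule used here.

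The calculations rest on the simplified study-size inputs: Norway is left out, all non-exposed time counts as unexposed although 7.3.1 sets part of it aside, and there is no confounder adjustment. The exact percentages would change with real data. The absence of a contrast between ages would not.

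**What to change.** 1. Keep the age-stratum IRRs with 95% CIs as planned.
2. In 7.7.2-7.7.4, add one Poisson model per outcome on the total population with DL exposure by age-group terms, letting confounder effects vary by age where needed. Report the ratios of IRRs between age groups with 95% CIs and the likelihood-ratio heterogeneity test.
3. For A-fib/flu, merge 0-4 with 5-19 years in that test, since only 0.64 events are expected at 0-4. The merged group has about 0.64 + 19.6 = 20.2.
4. Base any statement about age differences on the ratios of IRRs and their CIs, not on which strata are significant. State that a non-significant heterogeneity test is not evidence against a paediatric-specific effect, and give the reason: power is low at 0-4 years.
5. Amend the comment in Section 10 of the checklist to match.

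The cost is one extra model per outcome and a few sentences, with no new data. The downside is a test that is weak in the youngest group, which item 4 makes explicit.
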